5. SCREENING AND CONSENT

5.1 Informed Consent

It is the responsibility of the Investigator or delegate, to obtain written informed consent for each patient prior to performing any trial related procedure. A Patient Information Sheet is provided to facilitate this process. Investigators must ensure that they adequately explain the aim, trial treatment, anticipated benefits and potential hazards of taking part in the trial to the patient. The Investigator should also stress that the patient is completely free to refuse to take part or withdraw from the trial at any time. The patient should be given ample time (e.g. 24 hours) to read the Patient Information Sheet and to discuss their participation with others outside of the site research team. The patient must be given an opportunity to ask questions which should be answered to their satisfaction. The right of the patient to refuse to participate in the trial without giving a reason must be respected.

If the patient expresses an interest in participating in the trial they should be asked to sign and date the latest version of the Informed Consent Form. The Investigator or designate must then sign and date the form. A copy of the Informed Consent Form should be given to the patient, a copy should be filed in the hospital notes, and the original placed in the Investigator Site File (ISF). Once the patient is entered into the trial the patient's trial number should be entered on the Informed Consent Form maintained in the ISF. In addition, if the patient has given explicit consent a copy of the signed Informed Consent Form must be sent in the post to the Trials Office for review.

Details of the informed consent discussions should be recorded in the patient's medical notes, this should include date of, and information regarding, the initial discussion, the date consent was given, with the name of the trial and the version number of the Patient Information Sheet and Informed Consent Form. Throughout the trial the patient should have the opportunity to ask questions about the trial and any new information that may be relevant to the patient's continued participation should be shared with them in a timely manner. On occasion it may be necessary to re-consent the patient in which case the process above should be followed and the patient's right to withdraw from the trial respected. The patient should be given ample time to read changes made to the patient information sheet, and may re-consent at the same visit that new information is provided, if they wish to do so.

Electronic copies of the Patient Information Sheet and Informed Consent Form are available from the Trials Office and should be printed or photocopied onto the headed paper of the local institution.

Details of all patients approached about the trial should be recorded on the Patient Screening/Enrolment Log and with the patient's prior consent their General Practitioner (GP) should also be informed that they are taking part in the trial. A GP Letter is provided electronically for this purpose.

Translational Studies

Before proceeding with and/or collecting samples for either of the translational-studies, the informed consent procedure must be followed as directed for each translational-study.

5.2 Extension study

Patients enrolled as relapsed/refractory patients and treated with ibrutinib on the IcICLLe trial will be given the opportunity to join the IcICLLe extension study. Those who wish to join will be required to consent for this study via the IcICLLe extension study Patient Information sheet and consent form.

Patients who do not wish to enrol onto the extension study or those who are not eligible for it should continue to receive ibrutinib monotherapy and be followed up in accordance with Schedule A. Any additional safety information or changes relevant to the patients continuing on ibrutinib monotherapy will be given to patients in an addendum patient information sheet in order for them to re-consent and continue on study if they wish to do so.

5.3 Screening / Baseline

Following informed consent, the following samples will be provided for screening/baseline purposes:

5.3.1 Assessments 4 weeks prior to treatment start date

These assessments are to be performed **within the four weeks** prior to registration and following consent unless conducted as part of standard clinical practice.

Complete medical history: Detailed history of CLL, baseline clinical conditions

Complete physical examination:

- Blood pressure
- Pulse
- Temperature
- Height
- Weight
- ECOG performance status

Local laboratory tests:

Haematology:

- Haemoglobin
- Lymphocyte count
- Neutrophil count
- Platelet count
- Reticulocyte count
- White blood cell count (with differential count)

Biochemistry

- Albumin
- Alkaline Phosphatase (ALP)
- ALT or AST
- Calcium (adjusted)
- Creatinine
- eGFR
- Glucose
- LDH
- Phosphate
- Potassium
- Sodium
- Total Bilirubin
- Total Protein
- Urea
- Urate

Immunology:

- Direct coombs test
- Serum immunoglobulins and electrophoresis
- β_2 microglobulin concentration

Hepatitis B screening

- Minimum: HBsAg-status and HBcAb-status. These can be complemented with other appropriate markers as per local guidelines.
- HBV DNA PCR should be performed to if HBcAb is likely due to cross reactivity with IVIg. If this is negative the patient is eligible for screening. . Following the last dose of obinutuzumab, these patients should undergo HBV DNA PCR at all study visits for two years.

CT-scan: thorax, abdomen and pelvis to assess lymph node disease¹⁴

CT scans will be performed locally at IcICLLe trial sites. Reports may be requested for central review by members of the TMG. Redacted reports (where the patient is identified only by TNO) will be requested by email.

ECG: should be performed to assess patient for signs of atrial fibrillation

Constitutional symptom assessment: Assessments of fatigue, unintentional weight loss, fevers and night sweats.

Concomitant medication: Details should be recorded from 4 weeks before start of treatment.

¹⁴ If the patient has had a CT scan within 8 weeks of the proposed treatment start date this may be used as part of the screening process in order to reduce patient exposure to ionising radiation.

If there is any doubt regarding the immunological phenotype of the patients disease please send a peripheral blood sample to HMDS for evaluation at least two weeks prior to the screening bone marrow sample

5.3.2 Assessments 2 weeks before the treatment start date

These assessments are to be performed **within the two weeks** prior to registration and following consent

- **Clinical assessment of lymph node disease:**
 - The size of the largest lymph nodes in each nodal area (cervical, axillary and inguinal) should be measured in centimetres in 2-dimensions
- **Clinical assessment of liver and spleen:**
 - If palpable, size of liver and spleen below costal margin should be measured.
- **Pregnancy test** (in women of child bearing potential **within 2 weeks** prior to starting treatment)
- **Samples to send for central analysis** (see section 7.3 for details of how to do this):
 - 0.5 - 2 mL first-pull bone marrow aspirate
The first draw of bone marrow aspirate should be put in EDTA and is used for MRD flow cytometry (the less the marrow is diluted with blood the more accurate the assessment of involvement by CLL).
 - Bone marrow trephine biopsy (directly in formalin)
 - 4 x 5 mL peripheral blood in EDTA

Please note:

1. Samples sent for central analysis must be sent on Monday or Tuesday two weeks prior to the provisional treatment start date agreed with the IcICLLe trial office.
2. Confirmation by the HMDS that this two week peripheral blood sample is viable will be required before the patient starts treatment. If this sample is not viable, an additional peripheral blood sample will be requested and confirmed to be viable before the patient starts ibrutinib treatment.
3. IcICLLe Extension Study patients who are rolling over from IcICLLe and have undergone bone marrow examination within 6 months of starting the Extension Study are NOT required to have bone marrow examinations at screening

6. TRIAL ENTRY

Patients must be registered with the Cancer Research UK Clinical Trials Unit (CRCTU) at the University of Birmingham. The patient's eligibility will be confirmed at registration. If eligible for the study, the patient will be allocated a Patient Trial Number (TNO). The registration line will be open during office hours (9-5pm, Monday-Friday).

Registration line: [name]
Monday - Friday, 9-5pm

IcICLLe Extension Study

Relapsed/refractory patients who have received ibrutinib on IcICLLe who wish to join the extension study need to consent and (re-)register for the extension study. Ibrutinib naïve patients will need to consent and be registered for the IcICLLe extension study. **All patients entering the extension study will receive a new trial number (TNO).**

7. TREATMENT DETAILS

7.1 Trial Treatment

Ibrutinib and obinutuzumab are both Investigational Medicinal Products (IMPs) in this study.

All patients will receive continuous oral therapy with ibrutinib (420 mg OD) from registration until disease progression (as per the modified IWCLL response criteria (revised 2008) in appendix 2).

Patients in the IcCLLe extension study will additionally receive obinutuzumab intravenously for up to 6 cycles of therapy. This will be given at a dose of 1000 mg on days 1, 8, and 15 of cycle 1 and on day 1 of cycles 2-6 (see schedule A and B). If the patient becomes confirmed MRD negative they will also stop ibrutinib/obinutuzumab treatment (see section 7.2.3).

Please see Section 7.6 for supportive treatments for ibrutinib and obinutuzumab.

7.1.1 Ibrutinib treatment

Ibrutinib 420mg (3 x 140-mg capsules) should be taken orally once daily with the first dose taken on day 0 of treatment. The capsules are to be taken around the same time each day with 8 ounces (approximately 240 mL) of water. The capsules should be swallowed intact and patients should not attempt to open capsules or dissolve them in water. The use of strong CYP3A inhibitors/inducers, and grapefruit and Seville oranges should be avoided for the duration of the trial (Appendix 10). The use of Angiotensin-Converting Enzyme (ACE) inhibitors and Angiotensin Receptor Blockers (ARBs) are prohibited for patients receiving ibrutinib (Appendix 10).

- Patients who have a delay in administration of a dose of the study drug of <6 hours should take the planned dose as soon as possible after the intended time of administration. If the delay in administration of study drug is ≥6 hours, the dose should be skipped. Study drug administration may continue the next day at the usual time but the missed dose should not be made up.
- Vomited Ibrutinib doses may be retaken, but only if the capsule is visible in the vomit.
- If a patient experiences an ibrutinib overdose, consideration should be given as to whether ibrutinib administration should be temporarily interrupted. If the overdose ingestion is recent and substantial, use of gastric lavage or induction of emesis may be considered. Observation for any symptomatic side effects should be instituted, and biochemical and haematological parameters should be followed closely. Appropriate supportive management to mitigate adverse effects should be initiated.

Dose modifications and delays for ibrutinib are detailed in Section 7.4.1. Precautions for use are detailed in Section 7.8.

7.1.2 Obinutuzumab treatment

In patients who are ibrutinib naïve, ibrutinib 420mg/day should be started on Day 0 (24 hours before commencing obinutuzumab) to help reduce potential infusion reactions.

For monitoring of certain AEs, such as TLS, the results of the local haematology and biochemistry should be assessed by a delegated Investigator prior to subsequent infusion.

The most frequently observed AE in patients receiving obinutuzumab were IRRs which occurred predominantly during infusion of the first 1000 mg. In order to mitigate this, **appropriate premedication must be given (see Section 7.6.2).**

Dose modifications and delays for obinutuzumab are detailed in Section 7.4.2. Precautions for use are detailed in Section 7.9.

The initial dose of obinutuzumab should be split in accordance with the scheduled stipulated below (see also Table 1):

Cycle 1

Two infusion bags should be prepared for the infusion on Days 1 and 2 (100 mg for Day 1 and 900 mg for Day 2).. These will then be given as follows:

Day 1: 100 mg obinutuzumab intravenous infusion

- Administered at 25 mg per hour over 4 hours
- For the first dose given on day 1, if the first dose is completed without modifications of the infusion rate or interruptions, the second dose can be administered on the same day (as specified in Day 1 (continued) in Table 1 below)
- Appropriate time, conditions and medical supervision should be available throughout the infusion
- If there are any modifications of the infusion rate or interruptions during the first 100 mg the second dose must be administered the following day

Day 2: 900 mg obinutuzumab intravenous infusion (if not previously given on day 1)

- Administered at 50 mg per hour. In the absence of any infusion related reactions or hypersensitivity, the rate of infusion may be escalated in increments of 50 mg per hour every 30 minutes to a maximum rate of 400 mg per hour

Days 8 and 15: 1000 mg Obinutuzumab intravenous infusion

- Infusions may start at a rate of 100mg per hour and increase by 100mg/hr increments every 30 minutes to a maximum rate of 400mg per hour

Cycles 2-6

Days 29, 57, 85, 113 and 141

- All subsequent cycles will consist of one dose on the first day of the 28 day cycle

In the absence of any infusion related reactions or hypersensitivity, the rate of infusion for the administration of obinutuzumab in all subsequent cycles may start at a rate of 100 mg per hour and increased by 100 mg per hour increments every 30 minutes to a maximum rate of 400 mg per hour

Table 1: Obinutuzumab Schedule

Day of Treatment Cycle		Dose of Obinutuzumab	Rate of infusion (In the absence of infusion reactions/ hypersensitivity during previous infusions) ^a
Cycle1	Day 1	100 mg	Administer at 25 mg/hr over 4 hours. Do not increase the infusion rate.
	Day 2 or Day 1 (continued)	900 mg	If no infusion related reaction occurred during the prior infusion administer at 50 mg/hr. The rate of infusion can be escalated in increments of 50 mg/hr every 30 minutes to a maximum rate of 400 mg/hr. If the patient experienced an IRR during the previous infusion, start with administration at 25 mg/hr. The rate of infusion can be escalated in increments up to 50 mg/hr every 30 minutes to a maximum rate of 400 mg/hr.
	Day 8	1000 mg	If no infusion related reaction occurred during the prior infusion, when the final infusion rate was 100 mg/hr or faster, infusions can be started at a rate of 100 mg/hr and increased by 100 mg/hr increments every 30 minutes to a maximum of 400 mg/hr
	Day 15	1000 mg	
Cycles 2-6	Day 1	1000 mg	If the patient experienced an IRR during the previous infusion administer at 50 mg/hr. The rate of the infusion can be escalated in increments of 50 mg/hr every 30 minutes to a maximum rate of 400 mg/hr.

^a If an infusion reaction occurs, refer to Table 5 in Section 7.4.2.

Monitoring patients for Tumour Lysis Syndrome - Please refer to section 7.9.2 for further guidance Patients with a high tumour burden, high circulating absolute lymphocyte counts (greater than $25 \times 10^9/L$) or renal impairment (creatinine clearance of $< 70\text{ml/min}$) are considered at risk of TLS and should receive prophylaxis. Prophylaxis should consist of adequate hydration and administration of uricostatics (e.g., allopurinol) or suitable alternatives such as a urate oxidase (e.g., rasburicase), prior to the start of obinutuzumab infusion as per standard local practice. During the first cycles of obinutuzumab treatment, monitor the biochemistry of patients considered at risk for TLS. Should any early signs of TLS be detected, please treat the patient as per local practice.

Monitoring patients for thrombocytopenia

Patients who have a creatinine clearance of between 30 and 50 mL/min at baseline are at greater risk of developing thrombocytopenia. Clinics must perform full blood counts and biochemistry assessments before infusion, directly after infusion and the following morning after infusion

Patients should be closely monitored for thrombocytopenia, especially during the first cycle; regular laboratory tests should be performed until the event resolves, and dose delays should be considered in case of severe or life-threatening thrombocytopenia. Please refer to section 7.9.2 for further guidance.

Should any early signs of thrombocytopenia be detected, please treat the patient as per local practice.

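### After a Day 1 infusion reaction, the Day 2 bullet in Protocol Section 7.1.2 starts the 900 mg obinutuzumab dose at 50 mg/hr, while Table 1 of the same section requires 25 mg/hr

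*Protocol*

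**What the plan says.** Section 7.1.2 splits the first 1000 mg of obinutuzumab into 100 mg on Day 1 and 900 mg on Day 2, or 900 mg later on Day 1 if all goes well. It introduces the schedule with "The initial dose of obinutuzumab should be split in accordance with the scheduled stipulated below (see also Table 1").

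Two bullets decide when the 900 mg is given:

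- Same-day dosing is optional: "if the first dose is completed without modifications of the infusion rate or interruptions, the second dose can be administered on the same day".
- Otherwise Day 2 is compulsory: "If there are any modifications of the infusion rate or interruptions during the first 100 mg the second dose must be administered the following day".

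The start rate of the 900 mg then appears in two places:

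- Day 2 bullet: "Administered at 50 mg per hour. In the absence of any infusion related reactions or hypersensitivity, the rate of infusion may be escalated", in 50 mg/hr steps every 30 minutes to at most 400 mg/hr.
- Table 1, row for Day 2 or Day 1 (continued): "If no infusion related reaction occurred during the prior infusion administer at 50 mg/hr"; but "If the patient experienced an IRR during the previous infusion, start with administration at 25 mg/hr". After a reaction, "The rate of infusion can be escalated in increments up to 50 mg/hr every 30 minutes to a maximum rate of 400 mg/hr".

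The Table 1 rate column is headed "In the absence of infusion reactions/ hypersensitivity during previous infusions", although the cell beneath it states a rate for patients who did react.

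**The concern.** The bullet and the table give different instructions for the same dose in the same patient. The patients concerned have just reacted to the drug, and the instruction covers their next exposure to it. The protocol describes IRRs as the most frequent adverse event with obinutuzumab, arising mainly during the first 1000 mg, so the situation is foreseeable. A site or pharmacy that works from the bullets would start at the higher rate and could fairly say that it had followed the protocol.

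**Working it through.** No statistical figure is involved. The check compares the texts and adds simple arithmetic on rates.

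**Step 1. Which patients come under the Day 2 bullet?** Table 5 (Section 7.4.2) has the infusion slowed for a Grade 1-2 IRR, interrupted for a Grade 3 IRR, and therapy discontinued for Grade 4. A Day 1 reaction that is managed this way and does not end therapy is therefore a modification or interruption of the first 100 mg, and Section 7.1.2 then requires the 900 mg on Day 2. Patients without a reaction may also be dosed on Day 2, because the same-day option is not compulsory.

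**Step 2. Start rates side by side.**

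| Day 1 infusion | Day 2 bullet | Table 1 | Agree? |
|---|---|---|---|
| No IRR | 50 mg/hr | 50 mg/hr | Yes |
| IRR | 50 mg/hr | 25 mg/hr | No |

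**Step 3. Could the bullet's condition cover the start rate?** The sentence giving 50 mg/hr is complete before the condition begins, and the condition attaches to escalation. For cycles 2-6, by contrast, the text of the same section places the no-reaction condition ahead of the start rate.

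**Step 4. Does anything set precedence?** The pointer to Table 1 is general and gives no order. The one specific redirection to the table, for the continued Day 1 infusion, concerns same-day patients, whose first infusion ran unchanged. Table 5 sets rates within the infusion in which a reaction occurs and gives no start rate for the next infusion.

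**Step 5. Size at the start, after a Day 1 IRR.**

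- Ratio of start rates: 50 / 25 = 2.
- First 30 minutes, bullet: 50 mg/hr × 0.5 h = 25 mg.
- First 30 minutes, Table 1: 25 mg/hr × 0.5 h = 12.5 mg.
- Difference: 12.5 mg.

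**Step 6. What happens afterwards?** This depends on which infusion the bullet's condition on escalation refers to, and the bullet does not say.

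- *Current infusion only.* The bullet runs 50, 100, 150 mg/hr and so on; Table 1 at its fastest runs 25, 75, 125 mg/hr and so on. The bullet is 25 mg/hr faster at each step until the 400 mg/hr cap. At one hour it has delivered 25 + 50 = 75 mg, against 12.5 + 37.5 = 50 mg.
- *Prior infusion included.* A Day 1 reactor under the bullet stays at 50 mg/hr and has received 25 + 25 = 50 mg at one hour, the same as Table 1 at its fastest. From 30 minutes on, Table 1 permits the higher rate.

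The two-fold ratio is therefore a statement about the start only.

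**The case against.** The strongest defence is that the bullets state default rates and Table 1 states the exceptions. The table is in the same subsection, is signposted, and has a cell for exactly this case, so a specific conditional rule could reasonably be read as qualifying a general one. The bullet for Days 8 and 15 fits this pattern: it too gives only the default, 100 mg/hr, and leaves the 50 mg/hr post-reaction rate to the table. All patients also receive corticosteroid, analgesic and antihistamine premedication on Day 2 (Table 7), and ibrutinib-naïve patients start ibrutinib 24 hours before obinutuzumab to reduce reactions.

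Much of this stands as mitigation: a site that opens Table 1 finds the lower rate. But no sentence in Section 7.1.2 says that the bullets are defaults or that the table prevails, and the column heading, read literally, excludes the very patients whom the 25 mg/hr instruction addresses.

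Three stronger readings are tempting, and the protocol supports none of them:

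- *Table 5 shows the bullet to be wrong, because it limits the rest of the Day 1 infusion to 25 mg/hr after a reaction.* That is the ordinary Day 1 rate for everyone. Patients without a reaction also go from 25 to 50 mg/hr, under both sources, so the comparison does not show what rate is right after a reaction.
- *About 70% of patients are affected.* Section 1.4.1 reports IRRs in 238/336 (70.8%) of patients given obinutuzumab with chlorambucil. That counts all IRRs in a different regimen, not reactions to the first 100 mg in this one. It is background and does not size the affected group.
- *The conflict would raise the rate of severe reactions, or affect the primary endpoint or the toxicity stopping guideline.* Nothing in the protocol allows such an effect to be estimated.

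**Conclusion.** The point holds as a contradiction in operative dosing text that bears on patient safety; the Day 2 bullet is wrong as written. For a patient with an IRR during the first 100 mg, the bullet starts the 900 mg at 50 mg/hr and Table 1 at 25 mg/hr: a two-fold difference in starting rate, or 12.5 mg over the first 30 minutes. For patients without a Day 1 reaction the two sources agree. Only extension study patients, at most 40, receive obinutuzumab, and only those who react on Day 1 are touched; the protocol does not give their expected number.

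This rests on reading the bullet's condition as applying to escalation alone, as its punctuation indicates, and on finding no rule of precedence in the protocol. Which rate is clinically correct is not derived here. Table 1 is taken as the intended rule because it is the only source that addresses the post-reaction start. Sample size, error rates and analysis are unaffected.

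**What to change.** Reword the Day 2 bullet of Section 7.1.2 so that it carries the Table 1 exception and keeps the existing safeguard on escalation:

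- No IRR in the preceding infusion: begin at 50 mg/hr.
- IRR in the preceding infusion: begin at 25 mg/hr (Table 1).
- In both cases, escalate only while the current infusion is free of IRR and hypersensitivity, in steps of 50 mg/hr (up to 50 mg/hr after a prior IRR) every 30 minutes, to no more than 400 mg/hr. If a reaction occurs, follow Table 5.

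The third item matters: an amendment that added the 25 mg/hr start but dropped the condition on escalation would remove a protection that the bullet now has. Naming the current infusion also settles the ambiguity over which infusion the condition refers to.

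In addition, state in Section 7.1.2 that Table 1 governs infusion rates, and remove the no-previous-reaction limit from the heading of its rate column.

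The cost is protocol wording and a note to sites and pharmacy. No extra visits, data or patients are needed.
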